2.4.3.2 Compliance

Compliance for the open-label dose finding treatment period (OLDFI) will be assessed using the following parameters:

- The mean injection frequency of IMP OLDFI injections will be defined for each patient as the average number of days between 2 consecutive OLDFI injections, that is: (last OLDFI injection date – first OLDFI injection date)/(number of OLDFI injections -1) for patients receiving at least 2 OLDFI injections.
- The overall compliance for OLDFI injections will be defined for each patient as: 100- (%days with under-planned dosing + %days with above-planned dosing). Under-planned and above-planned dosing will be defined as follows, considering that injections should be performed every 2 weeks or every 4 weeks (± 3 days as per protocol):
 - The % days with under-planned dosing will be defined for each patient from Cohorts 1 & 2 as the number of days with no injection administered within the previous 17 days divided by the duration of IMP injection exposure in days. For example if a patient takes a dose 18 days after his/her previous injection, then 1 day is counted as a day under-planned dosing.
 - The % days with under-planned dosing will be defined for each patient from Cohorts 3 & 4 as the number of days with no injection administered within the previous 31 days divided by the duration of IMP injection exposure in days. For example if a patient takes a dose 32 days after his/her previous injection, then 1 day is counted as a day under-planned dosing.
 - The % days with above-planned dosing will be defined for each patient from Cohorts 1 & 2 as the number of days with more than one injection administered within the 11 days before divided by the duration of IMP injection exposure in days. For example if a patient takes a dose 9 days after his/her previous injection, then 2 days are counted as days above-planned dosing.
 - The % days with above-planned dosing will be defined for each patient from Cohorts 3 & 4 as the number of days with more than one injection administered within the 25 days before divided by the duration of IMP injection exposure in days. For example

if a patient takes a dose 23 days after his/her previous injection, then 2 days are counted as days above-planned dosing.

For the OLDFI/OLE combined period, only mean injection frequency will be assessed:

- For Cohorts 1 to 3, the mean injection frequency will be defined for each patient up to, and post switch of dose :
 - Up to the switch of dose, the average number of days between 2 consecutive injections is defined as (last injection date up to the switch – first injection date)/(number of injections up to the switch -1) for patients receiving at least 2 injections;
 - Post switch of dose, the average number of days between 2 consecutive injections is defined as (last injection date– first injection date post switch)/(number of injections post switch -1) for patients receiving at least 2 injections;
- For Cohort 4, the mean injection frequency will be defined for each patient for the entire period (no switch is planned for these patients):
 - The average number of days between 2 consecutive injections, defined as: (last injection date– first injection date)/(number of injections -1) for patients receiving at least 2 injections;

These parameters will be summarized descriptively (N, Mean, SD, Median, Minimum and Maximum).

The percentage of patients whose overall compliance is <80% will be also summarized as well as numbers and percentages of patients with 0%, >0% and $\leq 5\%$, >5% and $\leq 10\%$, >10% and $\leq 20\%$, and >20% days with above-planned dosing and numbers and percentages of patients with 0%, >0% and $\leq 5\%$, >5% and $\leq 10\%$, >10% and $\leq 20\%$, and >20% days with under-planned dosing.

According to protocol, cases of overdose are reported in the AE e-CRF pages and will be described in the AE analysis (see [Section 2.1.4.1](#) and [Section 2.4.5.1](#)). More generally, dosing irregularities will be listed in [Section 2.2.1](#).

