10.3.1 Temporary treatment discontinuation with investigational medicinal product(s)

Temporary treatment discontinuation (also referred to as treatment interruption) may be considered by the Investigator because of suspected AEs. Reinitiating of treatment with the IMP will be done under close and appropriate clinical/and or laboratory monitoring once the Investigator will have considered according to his/her best medical judgment that the responsibility of the IMP in the occurrence of the concerned event was unlikely and if the selection criteria for the study are still met (refer to [Section 7.1](#) and [Section 7.2](#)). All treatment interruption duration should be recorded by the Investigator in the appropriate eCRF screens when considered as confirmed.

Treatment interruption is defined as one or more scheduled injections that are not administered to the patient as decided by the Investigator.

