2.4.3.1 Extent of investigational medicinal product exposure

The total exposure to IMP will be assessed using the following parameters:

- Duration of OLDFI IMP injection exposure in weeks defined as (date of last OLDFI IMP injection – date of first OLDFI IMP injection + 14 days)/7 (for Cohorts 1& 2) or (date of last OLDFI IMP injection – date of first OLDFI IMP injection + 28 days)/7 (for Cohorts 3 & 4), regardless of unplanned intermittent discontinuations.
- The total number of OLDFI IMP injections by patient.
- For Cohorts 1 to 3, and for the OLDFI/OLE combined period the following parameters will be derived up to, and post switch of dose:
 - Duration of OLDFI/OLE combined period IMP injection exposure up to the switch to Phase 3 doses in weeks, defined as (date of last IMP injection up to the switch – date of first IMP injection + 14 days)/7 (for Cohorts 1& 2) or (date of last IMP injection up to the switch – date of first IMP injection + 28 days)/7 (for Cohorts 3 & 4), regardless of unplanned intermittent discontinuations.
 - Duration of IMP injection exposure post switch in weeks, defined as: (date of last IMP injection +14 – date of first IMP injection post switch)/7, regardless of intermittent discontinuations.
 - Total number of OLDFI/OLE combined period IMP injections up to, and post switch of dose.
- For Cohort 4, and for the OLDFI/OLE combined period, the following parameters will be derived:
 - Duration of OLDFI/OLE combined period IMP injection exposure in weeks, defined as (date of last IMP injection – date of first IMP injection + 28 days)/7, regardless of unplanned intermittent discontinuations.
 - Total number of OLDFI/OLE combined period IMP injections.
- For duration of IMP injection exposure calculation, see [Section 2.5.3](#) for calculation in case of missing or incomplete data. Non-integer values will be rounded to one decimal place.

Duration of OLDFI IMP exposure will be summarized descriptively as a quantitative variable (number, mean, SD, median, minimum, and maximum) and categorically using the following categories: ≥ 1 day to <1 week, ≥ 1 to <3 weeks, ≥ 3 to <5 weeks, ≥ 5 to <7 weeks, ≥ 7 to <9 weeks, ≥ 9 to <11 weeks, ≥ 11 weeks.

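### Overall compliance in SAP 2.4.3.2 cannot register a missed final dose, so in Cohort 3 it cannot register any missed dose

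*SAP*

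**What the plan says.** SAP 2.4.3.2 defines overall compliance for the open-label dose-finding (OLDFI) period as "100- (%days with under-planned dosing + %days with above-planned dosing", closing the bracket there. For Cohorts 1 and 2 the under-planned percentage is "the number of days with no injection administered within the previous 17 days divided by the duration of IMP injection exposure in days". For Cohorts 3 and 4 it is "the number of days with no injection administered within the previous 31 days divided by the duration of IMP injection exposure in days".

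The denominator comes from SAP 2.4.3.1. For the Q4W cohorts it is "date of last OLDFI IMP injection – date of first OLDFI IMP injection + 28 days)/7 (for Cohorts 3 & 4"; for the Q2W cohorts the corresponding term is "date of first OLDFI IMP injection + 14 days)/7 (for Cohorts 1& 2". SAP 2.5.1 takes the last injection as the last administration recorded in the OLDFI period, not the last one planned.

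Two further outputs follow from the measure or sit beside it. "The percentage of patients whose overall compliance is <80% will be also summarized". Mean injection frequency is also tabulated, but only for patients with at least two OLDFI injections.

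The protocol expects that doses can be skipped without treatment ending. In Section 10.3.1: "Treatment interruption is defined as one or more scheduled injections that are not administered to the patient as decided by the Investigator".

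**The concern.** Both parts of the under-planned percentage run over a period that closes shortly after the last injection given. A skipped injection can then count only if another OLDFI injection follows it. Two patients who each miss one dose get different scores according to which dose it was. Where the missable dose is always the last, as in Cohort 3, the score cannot move at all.

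What is at stake is the meaning of the compliance table and its <80% count. A reader takes 100% to mean that the planned treatment was given. Here it can describe a patient who received half of it, and the <80% count does not mean the same thing in each cohort.

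**Working it through.** **Inputs**

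- Limits for an under-planned day: 17 days (Q2W) and 31 days (Q4W). Limits for an above-planned day: 11 and 25 days. SAP 2.4.3.2.
- Exposure in days: last given − first given + 14 (Q2W) or + 28 (Q4W). SAP 2.4.3.1, with the last injection as defined in SAP 2.5.1.
- Planned injections: Weeks 0, 2, 4, 6 (Cohorts 1-2); Weeks 0, 4 (Cohort 3); Weeks 0, 4, 8 (Cohort 4). Protocol 6.1.

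**Formulas.** For each gap g between consecutive injections, under-planned days = g − 17 or g − 31 when positive, and above-planned days = 11 − g or 25 − g when positive. Compliance = 100 − 100 × (under + above) / exposure.

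**The SAP's own examples.** Q2W gap of 18 days: 18 − 17 = 1 under-planned. Q4W gap of 32 days: 32 − 31 = 1 under-planned. Q2W gap of 9 days: 11 − 9 = 2 above-planned. Q4W gap of 23 days: 25 − 23 = 2 above-planned. All four agree with the SAP.

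**After the last injection.** The tails are 14 and 28 days and the limits are 17 and 31 days. Since 14 < 17 and 28 < 31, no day after the last injection given can be under-planned.

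**Scores, other doses on schedule.** No above-planned days arise in these cases.

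| Cohort | Pattern | Under-planned / exposure (days) | Compliance |
|---|---|---|---|
| 3 | Week 4 missed | 0 / 28 | 100% |
| 3 | Week 4 given 7 days late (g = 35) | 4 / 63 | 93.7% |
| 3 | Week 4 given 14 days late (g = 42) | 11 / 70 | 84.3% |
| 4 | Week 8 missed | 0 / 56 | 100% |
| 4 | Weeks 4 and 8 missed | 0 / 28 | 100% |
| 4 | Week 4 missed (g = 56) | 25 / 84 | 70.2% |
| 1-2 | Week 6 missed | 0 / 42 | 100% |
| 1-2 | Weeks 4 and 6 missed | 0 / 28 | 100% |
| 1-2 | Only Week 0 given | 0 / 14 | 100% |
| 1-2 | Week 2 or Week 4 missed (g = 28) | 11 / 56 | 80.4% |

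The 7- and 14-day delays are illustrations. Protocol 8.1 and 8.1.2, in text on the extension, give those two different limits for a delayed Q4W injection, and the passages should be reconciled.

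**The <80% flag in Cohort 3.** One injection gives 100%. With two, under-dosing triggers the flag only if (g − 31)/(g + 28) > 0.2, that is 0.8g > 36.6, so g must be at least 46 days, or 18 days late. The flag can pick up a very late dose but not an absent one.

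**Another reading.** Suppose under-planned days were counted to the planned end of the period over the same exposure denominator. A Q2W patient with only Week 0 would have 56 − 17 = 39 days over 14, and a compliance of −178.6%. That reading does not work.

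**Mean injection frequency.** Cohort 4 without Week 8 gives 28/1 = 28 days, the same as complete dosing (56/2 = 28). Q2W without Week 6 gives 28/2 = 14, again unchanged (42/3 = 14). In Cohort 3 with one dose it is undefined.

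**Does the LDL-C estimate suffer?** SAP 2.3.1.1 and 2.4.4.1 keep values only up to the last OLDFI injection + 21 days (Q2W) or + 35 days (Q4W), counting the first injection as Day 1.

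- Cohort 3, Week 4 missed: the period ends on Day 36, and the Week 8 window opens on Day 43 (SAP 2.5.4).
- Cohorts 1-2, Week 6 missed: it ends on Day 50, before the Week 8 target of Day 57.
- Cohort 4, Week 8 missed: it ends on Day 64. The Week 8 sample (Day 57) is drawn before that dose and is unaffected. Week 10 and Week 12 samples on their target days (71 and 85) are excluded.

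**The case against.** The strongest reply is that this is a coherent choice: regularity is measured while the patient is exposed, and completion is reported elsewhere. The total number of OLDFI injections is summarized (SAP 2.4.3.1). The exposure categories put a one-dose Cohort 3 patient at 28/7 = 4 weeks rather than 56/7 = 8. Disposition lists patients who did not complete treatment (SAP 2.2). In Cohort 3 the N for mean injection frequency counts exactly those who had both doses. With about 10 patients per cohort, a missed dose would be found. All of this stands, and it limits the consequence. It does not repair a figure labelled overall compliance that ranks a dose never given above a late one.

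A reader might infer that the flaw hides the reason for the Cohort 3 result of −7.7%. The documents do not support that. The on-treatment cut-off removes the scheduled Week 8 value after a missed Week 4 dose. Protocol Section 4 reports the 8-week period completed in 31 patients, with no adverse event leading to permanent discontinuation, and offers insufficient dose as a likely explanation. Protocol 6.1 has both Cohort 3 injections given by site staff. Nothing suggests that doses were missed.

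It is also fair to say that a fixed planned-period denominator alone would not be enough. Late doses can push exposure past 56 or 84 days. Two missed Q2W doses would still score by position: Weeks 2 and 4 give 25/56, or 55.4%, and Weeks 2 and 6 give 22/56, or 60.7%. One missed dose would fall below 80% in the Q4W cohorts but not in Q2W (80.4%). The fix has to allow for this.

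**Conclusion.** The defect is real and follows from the stated formulas. With other doses on time, missed final doses leave overall compliance at 100% in every cohort, against 70.2% (Cohort 4) or 80.4% (Cohorts 1-2) for one missed middle dose. In Cohort 3 neither overall compliance nor its <80% flag can register a missed dose, and a dose 14 days late scores worse (84.3%) than one never given.

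Its reach is limited. Compliance is descriptive, defines no analysis population and does not enter the LDL-C model, so the LDL-C estimate is not biased by it. Missed doses are not lost from the report either. The figures assume that the remaining doses fall on their planned days, and that exposure in days is the SAP's exposure in weeks before division by 7. The point is worth correcting because a stated rule gives a misleading figure and the change is cheap.

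**What to change.** 1. Add injections received divided by injections planned (4 for Cohorts 1-2, 2 for Cohort 3, 3 for Cohort 4) to the compliance table for every patient, and report a <80% count on that ratio. One missed dose gives 3/4 = 75%, 1/2 = 50% and 2/3 = 67%, so it is flagged in every cohort whichever dose it was.
2. For patients without recorded permanent discontinuation, also count under-planned days, and set the denominator, to the later of the planned end of the OLDFI period (56 days for Cohorts 1-3, 84 days for Cohort 4) and the end of actual exposure. A missed final dose then scores 55.4% in Cohort 3 (56 − 31 = 25; 25/56), 70.2% in Cohort 4 (84 − 28 − 31 = 25; 25/84) and 80.4% in Cohorts 1-2 (56 − 28 − 17 = 11; 11/56). A Cohort 3 dose 14 days late keeps its 70-day denominator and its 84.3%, so late now ranks above missed.
3. Show permanent discontinuations in a separate row.
4. Label the existing measure *compliance while on treatment*.

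The day-based score will still differ by regimen and by the position of two missed doses. That is why the flag belongs on the injection ratio.

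The cost is SAP wording, slightly more programming and some less favourable compliance figures. Protocol 11.4.1.2 defines only injection frequency, so it need not change. The revision can be made before the final OLDFI analysis of Cohorts 1-4 described in SAP Section 3.

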The addition to the higher doses in the Q4W cohort with extended 12 week study duration (including 2 new visits at Week 10 and Week 12) for the open label dose-finding period will more appropriately ensure that steady state has been reached after 3 alirocumab injections (2 interdose intervals) in terms of PK and LDL-C and related parameter reduction efficacy. An intermediate visit between the dosing interval (Week 10) is specifically introduced to better document the PK and LDL-C data from the Q4W dosing regimen that is known to show some peak-trough variability over the 4-week dosing interval, ie, a peak in the decrease at the mid dosing interval time point and trough reduction in LDL-C at the end of dosing interval time period. Thus, extending the duration of a higher Q4W dosing regimen to 12 weeks (an additional 4 weeks) will secure more comprehensively data on the LDL-C related profile reduction potential of a Q4W dosing regimen for alirocumab.

Given the 12 week duration, only LDL-C and key related parameters (TC, non-HDL-C, and TG) will be measured at Week 10 and Week 12 to minimize blood collection. The post-treatment follow-up period is no longer needed based on the data collected from the previous 3 cohorts.

All patients in Cohort 4 will receive alirocumab at 150 mg Q4W for BW <50 mg/300 mg Q4W for BW \geq 50 kg using prefilled syringes.

Cohort 4, similar to the other cohorts, will include alirocumab administration during the open-label extension that will continue until approximately 10 weeks before the initiation of the pediatric phase 3 study or December 2018 at the latest. The patients, after a wash-out period of at least 10 weeks after the last injection of alirocumab, will have the opportunity to participate in the phase 3 study. Though Cohorts 1 to 3 will be switched to the optimal regimen selected for the phase 3 study, Cohort 4 will remain on their initial regimen given the planned study end date of December 2018.

Conclusion on the benefit risk assessment with alirocumab:

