8 STUDY TREATMENTS

8.1 INVESTIGATIONAL MEDICINAL PRODUCT(S)

For Cohorts 1 to 3, sterile alirocumab drug product will be supplied at a concentration of 150 mg/mL as 1.2 mL minimum extractable volume in a 3 mL vial filled with 1.9 mL solution for the main treatment period and in 3 mL vials (or in prefilled syringes if available) for patient included in the extension period.

A detailed manual for alirocumab solution preparation will be provided to the pharmacist (or equivalent) for individual dose preparation.

For Cohort 4, sterile alirocumab drug product will be supplied at a concentration of 150 mg/mL as 1 mL volume in a prefilled syringe (PFS).

Main treatment period (Open-Label, Repeated Dose-Finding, Sequential Group):

The different doses prepared according to the cohort and the body weight will be:

- For Cohort 1: 30 mg Q2W for BW <50 kg and 50 mg Q2W for BW \geq 50 kg.
- For Cohort 2: 40 mg Q2W for BW <50 kg and 75 mg Q2W for BW \geq 50 kg.
- For Cohort 3: 75 mg Q4W for BW <50 kg and 150 mg Q4W for BW \geq 50 kg.
- For Cohort 4: 150 mg Q4W for BW <50 kg and 300 mg Q4W for BW \geq 50 kg.

The body weight assessed at inclusion visit will be the reference for alirocumab solution preparation.

For Cohorts 1 & 2: The study treatment is a single SC injection of 0.5 mL for 30, 40, 50 or 75 mg dose of alirocumab (according to the cohort and the body weight) extracted from vials, administered every 2 weeks in the abdomen, thigh, or outer area of the upper arm.

For Cohort 3: The study treatment is a single SC injection of 1 mL for 75 or 150 mg dose of alirocumab (according to the body weight) extracted from vials, administered every 4 weeks in the abdomen, thigh, or outer area of the upper arm.

For Cohort 4, sterile alirocumab drug product will be supplied at a concentration of 150 mg/mL as 1 mL volume in a prefilled syringe (PFS).

For Cohort 4: The study treatment is a single SC injection of 1 mL for 150 mg dose of alirocumab and 2 injections of 1 mL containing 150 mg each to provide a total 300 mg (2 mL) of alirocumab through PFS administered every 4 weeks in the abdomen, thigh, or outer area of the arm.

Dosing for the main dose finding treatment period should ideally be administered Q2W SC or Q4W SC at approximately the same time of the day; however, it is acceptable to have a treatment window of \pm 3 days. The time of day is based on the patient's preference.

Open-label extension (OLE) treatment period:

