10.1.2.3 Visit 4/Week 4 (Day 28 ±3) at clinical site

- Collect AEs.
- Record concomitant medication.
- Get body weight measurement.
- IVRS/IWRS contact.
- Review patient's diet. Patient should be on a diet in accordance with the American Academy of Pediatrics guidelines (1) or equivalent.
- Take vital signs including HR and BP.
- Check of stability of background LMT.
- Obtain fasting blood sample for:
 - Liver panel (ALT, AST, ALP, and total bilirubin),
 - Hematology: red blood cell count including hematocrit, hemoglobin, WBC count with differential count and platelets,
 - Chemistry: glucose, sodium, potassium, chloride, bicarbonate, calcium, phosphorous, urea nitrogen, creatinine, uric acid, total protein, LDH, albumin, and γGT,

- Lipids: total-C, calculated LDL-C, HDL-C, TG, non-HDL-C,
- CPK,
- Serum alirocumab concentration (PK),
- PCSK9 levels (free and total).
- For Cohorts 1 & 2: The third alirocumab injection will take place at the study site, but only after the assessment of all evaluations planned at that visit. For Cohort 3: the second and last alirocumab injection of this period will take place at the study site, but only after the assessment of all evaluations planned at that visit.
- For Cohort 4, the second injection out of 3 of this period will take place at the study site.
- Reminder:
 - An appointment will be given for the next study site visit or visit at patient's home.

10.1.2.4 Visit 5/Week 6 (Day 42 ±3) at clinical site or nurse visit at patient's home. For Cohorts 3 and 4, a phone call may be done instead.

- Collect AEs.
- Record concomitant medication.
- IVRS/IWRS contact.
- Check of stability of background LMT.
- For Cohorts 1 & 2: The fourth and the last alirocumab injection for this period will take place at the study site or the patient's home, but only after the assessment of all evaluations planned at that visit (no injection for Cohort 3 or 4 at this visit).
- Reminders:
 - An appointment will be given for the next study site visit,
 - Remind patient to be in fasting conditions (ie, overnight, at least 8-hour fast and refrain from smoking) for next study site visit. Also, alcohol consumption within 48 hours and intense physical exercise within 24 hours preceding the next study site visit are discouraged.

10.1.2.5 Visit 6/Week 8 (Day 56 ±3)/ at clinical site (end of the OL dose finding treatment period)

- Collect AEs.
- Record concomitant medication.

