1.4 STUDY PLAN

The following figures present the graphical study design:

Figure 1 - Graphical study design (main phase, Cohorts 1 to 3)

[figure not shown]
[figure not shown]

Figure 2 - Graphical study design (main phase, Cohort 4)

* Inclusion (I): The inclusion or entry into the open-label dose finding treatment period for Cohort 4.

** The main phase for Cohort 4 will include 3 alirocumab injections (at W0, W4, and W8).

*** For Cohort 4, the study duration includes an extended 12 week treatment period, including a Week 10 visit, but will not have a follow up period, in contrast to the study design for Cohorts 1, 2, and 3.

**** Week 12 is the end of the open-label dose finding treatment period and possible entry point into the extension for Cohort 4.

Figure 3 - Graphical study design (optional extension phase, Cohorts 1 to 3)

[figure not shown]
[figure not shown]

Figure 4 - Graphical study design (optional extension phase, Cohort 4)

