2.3.2 Safety population

The Safety population considered for safety analyses in the OLDFI period and in OLDFI/OLE combined period will be the included population who actually received at least one dose or part of a dose of the IMP injection. Patients will be analyzed according to the dose of alirocumab actually received (ie, as-treated dose group, alirocumab 30 mg Q2W, alirocumab 40 mg Q2W, alirocumab 50 mg Q2W, alirocumab 75 mg Q2W, alirocumab 75 mg Q4W, alirocumab 150 mg Q4W [BW <50 kg], alirocumab 150 mg Q4W [BW ≥50 kg] or alirocumab 300 mg Q4W).

In addition:

- Included patients for whom it is unclear whether they took the study medication will be included in the safety population as assigned by IVRS.

- For patients receiving the 2 alirocumab doses planned for the cohort during the treatment period (cases reported as protocol deviation), the alirocumab dose used for as-treated analysis will be the one to which the patient was treated with the highest number of injections; in case of the same number of injections of each dose received the as-treated dose will be the as-randomized dose.

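### Does counting injections make the SAP's compliance rules misclassify correctly dosed 300 mg Q4W patients, whose every dose is two injections?

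*SAP*

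**What the plan says.** Several SAP rules that apply to Cohort 4 count injections.

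- **SAP 2.4.3.2 (Compliance).** Overall compliance is 100 minus the percentages of days under and above plan. For Cohorts 3 and 4 the above-plan numerator is "the number of days with more than one injection administered within the 25 days before". Mean injection frequency is the span from first to last injection divided by the number of injections minus one. Among the summaries: "The percentage of patients whose overall compliance is <80% will be also summarized".
- **SAP 2.4.3.1 (Exposure).** One listed parameter is "The total number of OLDFI IMP injections by patient".
- **SAP 2.3.2 (Safety population).** A patient who received both doses planned for the cohort is analysed under "the one to which the patient was treated with the highest number of injections", with ties going to the assigned dose.
- **SAP 2.4.5.1 (Adverse events).** Injection-site reactions are also expressed per injection.

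Protocol 8.1 describes the 300 mg dose as "2 injections of 1 mL containing 150 mg each to provide a total 300 mg (2 mL) of alirocumab". Elsewhere the word means a dosing occasion:

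- SAP 1.4, note to Figure 2: "The main phase for Cohort 4 will include 3 alirocumab injections (at W0, W4, and W8".
- Protocol 4, Cohort 4 rationale: "3 alirocumab injections (2 interdose intervals".
- Protocol 10.1.2.3, Week 4 visit: "the second injection out of 3 of this period will take place at the study site".

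**The concern.** In Cohorts 1 to 3 every main-phase dose is one injection, so syringe and occasion coincide. Cohort 4 was added later (amendment 2, 11-Dec-2017) and is the first to include a dose needing two. SAP version 2 extended the four-weekly compliance rules to it without stating what is counted.

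Taken syringe by syringe, every correct 300 mg administration puts two injections inside the 25-day look-back on the day it is given. All correctly dosed patients in that group would then be tabulated below 80% compliance and in the highest above-planned category (over 20% of days). The injection count would double, the mean interval would fall to well under half, and the denominator for injection-site reactions would be 6 rather than 3. A few patients with mixed dosing could also change as-treated group. A reader of the report could conclude that the highest-dose group had been badly dosed.

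**Working it through.** **Inputs.** Look-back of 25 days, under-plan limit of 31 days, and exposure equal to last minus first injection date plus 28 days (SAP 2.4.3.1 and 2.4.3.2). Cohort 4 doses at Weeks 0, 4 and 8, that is days 0, 28 and 56.

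**Reproducing the SAP's examples.** With a 25-day look-back, two injections separated by a gap *g* shorter than 25 days produce 25 − *g* above-plan days. For *g* = 23 this is 25 − 23 = 2, the SAP's figure. The two-weekly rule (11 days) with a gap of 9 gives 11 − 9 = 2, again the SAP's figure. A 26-day inclusive window would give 3 in both cases, so it is not what the SAP means.

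**300 mg patient dosed exactly on schedule.** Exposure = 56 + 28 = 84 days. No day is under plan on either reading.

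| | By syringe | By occasion |
|---|---|---|
| Injections | 6 | 3 |
| Above-plan days | 3 × (25 − 0) = 75 | 0 |
| Percent above plan | 75/84 = 89.3% | 0% |
| Compliance | 100 − 89.3 = 10.7% | 100% |
| Mean interval | 56/5 = 11.2 days | 56/2 = 28 days |

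**At the edges of the ±3-day allowance, by syringe.**

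- 25-day spacing: exposure 50 + 28 = 78 days, 75/78 above plan, compliance 3.8%.
- 31-day spacing: exposure 62 + 28 = 90 days, 75/90 above plan, compliance 16.7%.

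By occasion, compliance stays at 100% in both.

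**Combined period.** The first Cohort 4 patient is planned for 01-May-2018 (SAP 1.5) and last injections fall in December 2018 (Protocol 6.2.1). The last four-weekly dose in 2018 is then at Week 32: 9 occasions, 18 syringes, 224 days. The mean interval is 224/17 = 13.2 days by syringe and 224/8 = 28 days by occasion.

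**As-treated group.** Take every mixed 150/300 mg sequence over two or three occasions, for each assigned dose: 2 × 2 + 6 × 2 = 16 cases. The two readings differ in 5, always towards 300 mg:

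- One dose of each with 150 mg assigned: a tie by occasion, 1 v 2 by syringe (2 orders).
- Two 150 mg doses and one 300 mg dose with 300 mg assigned: 2 v 1 by occasion, a tie by syringe (3 orders).

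All 16 cases are protocol deviations.

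**Which reading the SAP supports.** Its explicit count for Cohort 4 is three injections at three visits. The compliance section introduces its rules on the premise that injections occur two or four weeks apart, which two syringes on one day cannot satisfy. Its examples speak of a dose taken so many days after the previous injection, using the two words for one event. The quantity is named as dosing above plan, and a planned 300 mg dose is not above plan. The syringe sense appears only in the protocol, where the product and its administration are described.

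**The case for a change.** The strongest reply is that intent does not write the program. Injection dates come from an administration page in the e-CRF, and the documents do not show whether it holds one record or two per 300 mg dose. If two, literal coding of the formulas would produce the 10.7% figure. For injection-site reactions per injection, a syringe denominator is reasonable in itself, so intent cannot be inferred there, and the choice changes the rate twofold.

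What stands is that the unit is nowhere formally defined and that the site-reaction denominator could be either. What does not stand is that the compliance tables would plausibly come out wrong. An output showing every 300 mg patient between 3.8% and 16.7%, after three doses given by site staff on schedule, would be recognised at once as a counting artefact. The site-reaction rate needs only a footnote naming its unit.

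A related point concerns the overdose definition (Protocol 9.2.3.2 and 10.4.1.3). Its explanatory clause, about two or more injections from the kit within 14 days, sits awkwardly with a two-syringe dose and with the same sentence's criterion of at least double the intended dose; the two parts need to be read together. The sentence also says overdose is not based on systematic injection counts, and SAP 2.1.4.1 selects these events by MedDRA codes and tick boxes. A planned 300 mg dose therefore does not enter the overdose analysis by counting.

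**Conclusion.** No change to the plan is needed. The arithmetic of the syringe reading is right, but the SAP's own usage points to dosing occasions, and on that reading the compliance, frequency and as-treated rules give the expected results: 100%, 28 days, and no reclassification without a dosing deviation. What remains is a definition left implicit.

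The reach is small. Only the 300 mg group is affected, planned at 4 to 6 patients, and only in descriptive tables and, after a deviation, the safety grouping. The mITT population is analysed by IVRS-allocated dose, exposure duration uses dates only, and the LDL-C MMRM does not use compliance.

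This rests on one assumption: that whoever programs the tables follows the SAP's occasion usage, whatever the record layout of the e-CRF page, which the documents do not show.
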